9.2.1 Primary Efficacy Analysis

The primary endpoint is ACR20 response at Week 12. Analysis of the primary endpoint will be conducted on the FAS based on randomized treatment groups (upadacitinib 15 mg QD and the placebo group). Point estimate and 95% CI using normal approximation will be provided for the response rate for each randomized treatment group. Comparison of the primary endpoint will be made between the upadacitinib group and placebo group using the Cochran-Mantel-Haenszel test adjusting for stratification factor country. Point estimate, 95% CI using normal approximation and p-value for the treatment comparison will be presented. P-value is constructed using the Cochran-Mantel-Haenszel test. For the primary analysis, non-responder imputation (NRI) will be used.

9.2.2 Sensitivity Analysis of Primary Efficacy Variables

The primary analysis for point estimate and CI will be repeated using Observed Cases without any imputation as a sensitivity analysis. This will be conducted on the FAS based on randomized treatment groups.

Supportive NRI analysis will also be conducted on the Per Protocol Analysis Set.

9.2.3 Key Secondary Efficacy Analyses

Ranked key secondary endpoints (at Week 12) are:

1. Change from baseline in DAS28 (CRP);
2. Change from baseline in HAQ-DI;
3. Change from baseline in Short Form-36 (SF-36) Physical Component Score (PCS);
4. Proportion of subjects achieving LDA based on DAS28 (CRP) ≤ 3.2 ;
5. Proportion of subjects achieving Clinical remission (CR) based on DAS28 (CRP);
6. Proportion of subjects achieving LDA based on CDAI ≤ 10 ;

Other key secondary endpoints (at Week 12) are:

1. ACR50 response rate;
2. ACR70 response rate;
3. ACR20 response rate at Week 1.

For binary endpoints, frequencies and percentages will be reported for each randomized treatment group. Similar analyses as for the primary endpoint will be conducted.

For the major RA continuous endpoints DAS28 and HAQ-DI change from baseline, statistical inference will be conducted using analysis of covariance (ANCOVA) coupled with MI for missing data handling. Specifically, the ANCOVA model will include treatment as the fixed factor, and the corresponding baseline value and the stratification factor country as the covariates. For other continuous endpoints, statistical inference will be conducted using the MMRM model as described in Section 9.1.2, with the main stratification factor being country. From both the MI and MMRM analyses, the LS mean and 95% CI will be reported for each randomized treatment group; the LS mean treatment difference and associated 95% CI and p-value will be reported comparing upadacitinib group with the placebo group.

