4.2 Overall Study Design and Plan

This is a Phase 3 multicenter study that includes two periods. Period 1 is a 12-week, randomized, double-blind, parallel-group, placebo-controlled period designed to compare

the safety and efficacy of upadacitinib 15 mg QD versus placebo for the treatment of signs and symptoms of subjects with moderately to severely active RA from China, Brazil, and South Korea who are on a stable dose of csDMARDs and have an inadequate response to csDMARDs. Period 2 is an open-label 52-week extension period to evaluate the long-term safety, tolerability, and efficacy of upadacitinib 15 mg QD in subjects from China, Brazil, and South Korea who have completed Period 1.

The study is designed to enroll approximately 322 subjects at approximately 50 study centers in China, Brazil and South Korea to meet scientific and regulatory objectives without enrolling an undue number of subjects in alignment with ethical considerations. Therefore, if the target number of subjects has been enrolled, there is a possibility that additional subjects in screening will not be enrolled.

The study duration will include a 35-day screening period; a 12-week randomized, double-blind, parallel-group, placebo-controlled treatment period (Period 1); an open-label 52-week extension period (Period 2); and a 30-day follow-up period (visit or call).

Subjects who meet eligibility criteria will be randomized in a 1:1 ratio to one of two treatment groups. It is expected that approximately 222 subjects will enter the study from China and 100 subjects from other countries including Brazil and South Korea:

- Group 1: upadacitinib 15 mg QD (Period 1) → upadacitinib 15 mg QD (Period 2)
- Group 2: Placebo (Period 1) → upadacitinib 15 mg QD (Period 2)

Randomization will be stratified by country.

Subjects must have been on a stable dose of csDMARD(s) for ≥ 4 weeks prior to the first dose of study drug and must remain on a stable dose until Week 24; the csDMARD dose may be decreased only for safety reasons. At Week 24, if a subject fails to meet the Low Disease Activity (LDA) criterion (LDA defined as CDAI ≤ 10) the investigator should adjust the subject's background RA therapies. Starting at Week 24 (after Week 24

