4.3 Sample Size

The planned total sample size of 322 for this study provides over 90% power for a 21.7% difference in ACR20 response rate at Week 12 (assuming a placebo ACR20 response rate of 36.7%), at two-sided significance level of 0.05 and accounting for a 10% dropout rate. This sample size will also provide at least 90% power for most of the key secondary endpoints, including change from baseline in DAS28 (CRP), ACR50 response rate, LDA and CR based on DAS28 (CRP), and SF-36 PCS, at two-sided significance level of 0.05 and accounting for a 10% dropout rate.

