• Proportion of subjects achieving Clinical remission (CR) based on DAS28 (CRP) at Week 12	
 Point estimate, 95% CI and p-value for the treatment comparison between upadacitinib group and placebo group using the Cochran-Mantel-Haenszel test adjusting for stratification factor country. The 95% CI will be based on normal approximation.
• Proportion of subjects achieving LDA based on CDAI ≤ 10 at Week 12	
 Imputation: NRI for primary analysis and OC for sensitivity analysis
• ACR50/70 response at Week 12	
 Analysis Set: FAS
• ACR20 response at Week 1	

Table 7. Summary of Efficacy Variables and Corresponding Analyses for Efficacy Analysis in Period 1 (Continued)

Efficacy Variables	Analysis Method
Key Secondary Variables (continued)	
Continuous Endpoints:	
• Change from baseline in DAS28(CRP) at Week 12	
 LS mean, and 95% CI within each treatment group and LS mean, 95% CI and p-values between upadacitinib group and the placebo group using ANCOVA model with treatment, country and baseline value as covariates. Imputation: MI Analysis Set: FAS
• Change from baseline in SF-36 Physical Component Score (PCS) at Week 12	
 LS mean and 95% CI within each treatment group and LS mean, 95% CI and p-values between upadacitinib group and the placebo group using MMRM model with fixed effects of treatment, visit and treatment-by-visit interaction, country and baseline value as covariate. Analysis Set: FAS
Additional Variables (Summarized at all Visits up to Week 12)	
Binary Endpoints:	
• ACR20/50/70 response rate	
 Point estimate and 95% CI of the response rate for each treatment group. The 95% CI will be based on normal approximation.
• Proportion of subjects achieving change from baseline in HAQ-DI ≤ -0.22 for subjects with baseline HAQ-DI ≥ 0.22	
 Point estimate, 95% CI and p-value for the treatment comparison between upadacitinib group and the placebo group using the Cochran-Mantel-Haenszel test adjusting for stratification factor country. Only nominal p-value will be provided, and the 95% CI will be based on normal approximation.

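### Ranked endpoints 4 to 6 are absolute Week 12 cut-offs analysed without the baseline score that adjusts their continuous versions: a modest, avoidable loss of precision

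*SAP*

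**What the plan says.** SAP 9.2.3 ranks six key secondary endpoints. Ranks 4 to 6 are DAS28(CRP) at or below 3.2, DAS28(CRP) remission (below 2.6 in SAP 9.4.9) and CDAI at or below 10, all at Week 12. For binary endpoints it states: "Similar analyses as for the primary endpoint will be conducted". SAP Table 7 (section 9.2.7) gives the comparison as "using the Cochran-Mantel-Haenszel test adjusting for stratification factor country", with non-responder imputation (NRI) as primary and observed cases as sensitivity.

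SAP Appendix B supplies the estimate: the simple difference in proportions with a Wald interval that has no stratification term. The p-value therefore uses country and the interval does not. Neither uses a baseline disease-activity score.

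The continuous versions are treated differently. Change in DAS28(CRP), rank 1, is analysed by ANCOVA with treatment, country and baseline value (SAP 9.2.3). Change in CDAI, an additional endpoint and not a ranked one, is analysed by MMRM that also includes its baseline value (SAP 9.2.4).

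Randomization is stratified by country only (SAP 4.2). The baseline DAS28 subgroup in SAP Table 6 applies to the primary endpoint only. No baseline-adjusted analysis of ranks 4 to 6 is planned, even as a sensitivity analysis.

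**The concern.** ACR20 is defined by improvement from the subject's own baseline, so the starting level is partly built into it. Low disease activity and remission are not: they ask whether the Week 12 score lies below a fixed value. Entry sets a floor of 6 swollen and 6 tender joints but no ceiling (protocol 5.2.1), so subjects start at different distances from the threshold. If the Week 12 score is correlated with its baseline, the baseline predicts who crosses. Carrying the ACR20 method over unchanged then discards information that is already collected and derived (SAP 6.1).

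What is at stake is the width of the intervals for ranks 4 to 6. If the true effects were much smaller than expected, there would also be a little power, and a failure at rank 4 stops formal testing of ranks 5 and 6 (SAP 9.2.5).

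**Working it through.** **1. The plan's own power figure.** SAP 4.3 states: "The planned total sample size of 322 for this study provides over 90% power for a 21.7% difference in ACR20 response rate". Its inputs are a 36.7% placebo rate, a two-sided alpha of 0.05 and 10% dropout. Allocation is 1:1, so n = 161 per arm, or 161 × 0.9 ≈ 145 after dropout. The active rate is 36.7 + 21.7 = 58.4%. With d = p1 − p0 and p̄ the mean of the two rates:

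power = Φ( [d − 1.96·√(2p̄(1−p̄)/n)] / √([p1(1−p1) + p0(1−p0)]/n) )

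This gives 97.6% at n = 161 and 96.3% at n = 145, so the stated figure is reproduced.

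SAP 4.3 also says "This sample size will also provide at least 90% power for most of the key secondary endpoints", naming LDA and remission based on DAS28(CRP). Protocol Table 1 (Study M13-549, upadacitinib 15 mg v placebo) gives LDA 48% v 17% and remission 31% v 10%. At n = 145 the same formula gives above 99.99% and 99.5%.

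**2. The planned interval at those rates, 161 per arm.**
- LDA: 1.96 × √[(0.48×0.52 + 0.17×0.83)/161] = 1.96 × √(0.3907/161) = 9.66 points.
- Remission: 1.96 × √[(0.31×0.69 + 0.10×0.90)/161] = 1.96 × √(0.3039/161) = 8.52 points.

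**3. What baseline adjustment could gain.** The baseline-to-Week-12 correlation ρ is in neither document, so it is an assumption shown as a range. Let B be the standardised baseline, and let the Week 12 score be normal with correlation ρ to B. Assume 10% of subjects are non-responders through dropout unrelated to B, and read the Table 1 rates as already including them. The response probability given B in arm a is

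e_a(B) = 0.9 · Φ( (c_a − ρB)/√(1−ρ²) ), with Φ(c_a) = p_a/0.9.

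The variances, each to be divided by 322, are
- crude: V_c = 2p1(1−p1) + 2p0(1−p0);
- adjusted: V_a = E[ 2e1(1−e1) + 2e0(1−e0) + (e1 − e0 − d)² ].

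The half-width is 1.96·√(V/322). V_c is 0.7814 for LDA and 0.6078 for remission.

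| ρ (assumed) | LDA V_a | LDA variance cut | LDA half-width (from 9.66) | Remission V_a | Remission variance cut | Remission half-width (from 8.52) |
|---|---|---|---|---|---|---|
| 0.20 | 0.7669 | 1.9% | 9.57 | 0.5976 | 1.7% | 8.44 |
| 0.37 | 0.7315 | 6.4% | 9.34 | 0.5722 | 5.9% | 8.26 |
| 0.48 | 0.6969 | 10.8% | 9.12 | 0.5466 | 10.1% | 8.08 |
| 0.58 | 0.6567 | 16.0% | 8.85 | 0.5160 | 15.1% | 7.85 |

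For LDA this corresponds to an effective total of 322 × 0.7814/V_a, about 328 to 383 subjects. Ignoring dropout would overstate the LDA cuts, at 2.2%, 7.5%, 12.8% and 18.9%.

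**4. Simulation check** (3,000 trials per setting, 161 per arm, no dropout, country split per arm assumed 111/25/25). The country-stratified CMH test was compared with a logistic model on treatment, country and baseline.
- Variance cut at ρ = 0.3 and 0.5: LDA 3.9% and 14.0% (no-dropout formula 4.9% and 13.9%); remission 4.1% and 12.2% (formula 4.2% and 12.3%).
- Type I error at 17% in both arms: CMH 4.9% and 4.9%; logistic 4.7% and 5.4%.
- LDA effect halved (17 + 31/2 = 32.5% v 17%): CMH power about 90%; logistic about 92% and 94%. The logistic test here was the Wald test of the treatment coefficient.

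**5. Rank 6.** The documents give no CDAI LDA rates, so no size can be computed.

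**The case against.** The strongest reply is that this is a preference about efficiency. CMH stratified by the only randomization factor is a valid test, its type I error is unaffected, and at the Table 1 rates no ranked decision is likely to change. All of that stands.

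A reader might infer more, and the documents do not support it:

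- *That crossing the threshold depends strongly on baseline.* Neither document gives a baseline SD, a residual SD or a correlation. At ρ = 0.2 the LDA half-width moves by about 0.1 point.
- *That chance baseline imbalance is a separate harm or a bias.* Under randomization it is part of the sampling variance that the Wald interval already covers. It is the same precision point seen from another side. Baseline DAS28 and CDAI will also be tabulated by arm (SAP 6.1).
- *That a size has been shown for all three endpoints.* It has been shown for ranks 4 and 5 only.

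Two practical objections also stand. CMH is in the protocol as well as the SAP (Synopsis, 8.1.4.1.1 and 8.1.4.1.2), so replacing it as the test is a protocol departure. And DAS28 or CDAI is missing when any component is missing (SAP 9.4.6, 9.4.8): a subject with no baseline score still counts under CMH with NRI but would drop out of a regression model unless a rule is given, contrary to analysis on the FAS (SAP 9.1).

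None of this explains why the baseline score is used for the continuous measures and left out of the threshold versions.

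**Conclusion.** The point holds as a low-cost improvement. Ranks 4 to 6 are analysed without a covariate that the SAP itself uses for the same measures. The planned test is valid, the estimate is unbiased, and power for ranks 4 and 5 exceeds 99% at the Table 1 rates.

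The loss is a variance about 2% to 16% larger than necessary for LDA and about 2% to 15% for remission, or roughly 0.1 to 0.8 points on an LDA half-width of 9.7. Power would matter only if the effect were far smaller than in Study M13-549: about 2 to 4 points if the LDA effect were halved, before any allowance for dropout.

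These sizes rest on a latent-normal model, an assumed ρ of 0.2 to 0.58, 10% dropout unrelated to baseline, and rates borrowed from Study M13-549. For rank 6 the direction is plausible but the size is unknown.

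**What to change.** Amend SAP 9.2.3, Table 7 and Appendix B before the Period 1 database lock:

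1. For ranks 4 to 6, estimate the risk difference and 95% CI from a logistic model with treatment, country and the continuous baseline score: DAS28(CRP) for ranks 4 and 5, CDAI for rank 6. Standardise the predictions over the whole FAS.
2. Name the variance method, delta-method or sandwich.
3. Keep NRI for the outcome. Fill a missing baseline score by a simple rule that ignores treatment, for example the overall mean, so that no FAS subject is dropped.
4. State which p-value enters the step-down sequence. Either use the model's p-value, record it as a change from the protocol and keep CMH as supportive; or keep the CMH p-value for the sequence and report the standardised difference and CI as the estimate. The second choice leaves the protocol's test untouched and still delivers the narrower interval.

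The cost is SAP wording and slightly more programming than CMH, plus a documented protocol departure if the p-value changes. No new data or visits are needed. Timing matters, because covariates added after unblinding would look chosen on the results.

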#### **8.1.4.1.5 Imputation Methods**

The following methods will be used for missing data imputation:

**Observed Cases (OC):** The OC analysis will not impute values for missing evaluations, and thus a subject who does not have an evaluation on a scheduled visit will be excluded from the OC analysis for that visit.

**Multiple Imputation (MI):** The MI analysis imputes missing data multiple times under appropriate random variation and thus generates multiple imputed "pseudo-complete" datasets. Results will be aggregated across the multiple imputed datasets, overcoming drawbacks of the single imputation methods.

**Non-Responder Imputation (NRI):** NRI applies to binary endpoints only. In NRI analysis, subjects who prematurely discontinue study drug will be considered non responders after discontinuation.

The NRI approach will serve as the primary analysis approach for key binary endpoints. The MI approach will serve as the primary analysis approach for key continuous endpoints. Sensitivity analyses based on OC will also be conducted for key endpoints.

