## **8.2 Determination of Sample Size**

The planned total sample size of 322 for this study provides over 90% power for a 21.7% difference in ACR20 response rate (assuming a placebo ACR20 response rate of 36.7%), at two-sided significance level of 0.05 and accounting for a 10% dropout rate. This sample size will also provide at least 90% power for most of the key secondary endpoints, including change from baseline in DAS28(CRP), ACR50 response rate, LDA and CR based on DAS28(CRP), and SF-36 PCS, at two-sided significance level of 0.05 and accounting for a 10% dropout rate.

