The MI analysis will impute missing data multiple times under appropriate random variation and thus generate multiple imputed "pseudo-complete" datasets. Results will be aggregated across the multiple imputed datasets, overcoming drawbacks of the single imputation methods. PROC MI will be used to generate 5 datasets using the fully conditional specification (FCS) method. Specifically, treatment group is included in the FCS imputation model to enable sampling stratified by treatment groups. Additionally, the imputation model includes demographics variables and baseline disease characteristics, as well as longitudinal response observed at any other visits. An ANCOVA model will first be performed on each of the multiple imputed datasets adjusting for treatment, stratification factor and baseline value. PROC MIANALYZE will then be used to aggregate the results for the final statistical inference using Rubin's method. The imputation is based on assumption of data being missing at random. The missing at random assumption is considered reasonable given the high placebo response rate typically seen in RA trials. Additionally, in RA trials, the proportion of discontinuation is relatively small (10 – 15% only) and the rate of discontinuation due to lack of efficacy is generally low (< 5%).

9.2 Efficacy Analysis for Period 1

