9.2.5 Handling of Multiplicity

In order to preserve Type I error, a step-down approach will be used to test the primary and ranked key secondary endpoints where statistical significance can be claimed for a lower ranked endpoint only if the previous endpoint in the sequence meets the requirements of significance. Specifically, the testing will utilize the endpoint sequence

of primary endpoint followed by ranked key secondary endpoints in the order as specified in Section 9.2.3, using α of 0.05.

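### DAS28(CRP) and HAQ-DI, the first two ranked gates, are tested with only 5 imputations and no stated seed, so a p-value near 0.05 is not reproducible

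*SAP*

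**What the plan says.** SAP 9.2.5 tests the primary endpoint and then the "ranked key secondary endpoints in the order as specified in Section 9.2.3, using α of 0.05". The rule is that "statistical significance can be claimed for a lower ranked endpoint only if the previous endpoint in the sequence meets the requirements of significance". Ranks 1 to 3 in SAP 9.2.3 are change in DAS28(CRP), HAQ-DI and SF-36 PCS. The DAS28(CRP) low disease activity, DAS28(CRP) remission and CDAI low disease activity endpoints follow.

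For DAS28 and HAQ-DI, SAP 9.2.3 uses ANCOVA with multiple imputation (MI), pooled by Rubin's method. Section 9.1.2 sets the number of imputations: "PROC MI will be used to generate 5 datasets using the fully conditional specification (FCS) method". It gives no seed and describes the imputation covariates by class, without a variable list.

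For SF-36 PCS the SAP says: "For other continuous endpoints, statistical inference will be conducted using the MMRM model as described in Section 9.1.2". Table 7 repeats this and Appendix C gives model code.

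Protocol 8.1.4.1.2 specifies ANCOVA for the continuous key secondary endpoints. Protocol 8.1.4.1.5 adds: "The MI approach will serve as the primary analysis approach for key continuous endpoints", and "Sensitivity analyses based on OC will also be conducted for key endpoints". Neither section makes an exception for SF-36 PCS.

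**The concern.** MI draws random numbers. With 5 draws, the pooled estimate and its variance both move when the seed changes, and so does the p-value. At ranks 1 and 2 that p-value is a gate: DAS28(CRP) stands before five later ranked endpoints and HAQ-DI before four. If either falls near 0.05, an unrecorded seed could decide whether the later claims are open, and nobody could regenerate the result from the SAP alone.

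The protocol and SAP also name different methods for rank 3, which stands before three endpoints, and the SAP does not say that it departs from the protocol.

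**Working it through.** **The plan's own figure.** Protocol 8.2 states: "The planned total sample size of 322 for this study provides over 90% power for a 21.7% difference in ACR20 response rate", "at two-sided significance level of 0.05 and accounting for a 10% dropout rate". With 161 per arm and 10% dropout, n = 161 × 0.9 ≈ 145. For 58.4% against 36.7% (mean 0.4755), power = Φ[(0.217√145 − 1.96√(2 × 0.4755 × 0.5245)) / √(0.584 × 0.416 + 0.367 × 0.633)] = Φ[(2.613 − 1.384)/0.689] = Φ(1.78) = 96.3%. The stated bound holds. The documents give no effect or SD for the continuous endpoints, so everything below rests on assumed standardised effects.

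**Seed noise in the test statistic.** Let W and B be the within- and between-imputation variances, T = W + (1 + 1/m)B, and γ = (1 + 1/m)B/T the fraction of missing information. I take γ = 10–15%, in line with the 10–15% discontinuation quoted in SAP 9.1.2. Two parts add:

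- The pooled estimate has seed variance B/m, which adds γ/(m + 1) to the variance of Z.
- B is estimated on m − 1 degrees of freedom, which adds [(z/2) γ √(2/(m − 1))]².

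At z = 1.96, m = 5 and γ = 0.10: √(0.10/6 + (0.98 × 0.10 × 0.707)²) = √(0.0167 + 0.0048) = 0.147.

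| m | Seed SD of Z, γ = 10% | γ = 15% | Relative efficiency 1/(1 + γ/m) |
|---|---|---|---|
| 5 | 0.147 | 0.189 | 0.98–0.97 |
| 50 | 0.049 | 0.062 | 0.998–0.997 |
| 100 | 0.034 | 0.044 | 0.999 |

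**How often two seeds disagree on p<0.05.** Simulation: 161 per arm; baseline, Week 4 and Week 12; missing-at-random dropout; imputation by arm; m = 5; 500 datasets per cell.

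| Assumed effect (SD) | Power at 10% / 15% missing | Seeds disagree, 10% missing | 15% missing |
|---|---|---|---|
| 0.22 | 49% / 45% | 6.8% | 7.2% |
| 0.30 | 77% / 71% | 7.4% | 6.0% |
| 0.377 | 91% / 91% | 2.6% | 3.8% |
| 0.50 | 99% / 99% | 0.2% | 0.4% |

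Standard errors are about 1.1–1.2 points in the upper two rows (for example √(0.074 × 0.926/500) = 1.2%) and 0.7–0.9 in the third. The last row is 1 and 2 datasets.

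A formula check needs no simulation. If s is the seed SD of Z, two seeds differ on average by 2s/√π = 1.128s, so they straddle 1.96 with probability of about φ(Φ⁻¹(power)) × 1.128s. At 91% power, φ = 0.162. With m = 5 this gives 0.162 × 1.128 × 0.147 = 2.7% and, with s = 0.189, 3.5%, matching the third row. With m = 50 (s = 0.049–0.062) it gives 0.9–1.1%, and with m = 100 (s = 0.034–0.044) 0.6–0.8%.

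**Single datasets, many seeds** (central 95% range of p; reference p from 200 imputations):

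| Reference p | γ | m = 5 | m = 100 |
|---|---|---|---|
| 0.046 | 8% | 0.026–0.089 | 0.041–0.054 |
| 0.055 | 14% | 0.027–0.143 | 0.048–0.070 |
| 0.028 | 15% | 0.009–0.066 | 0.020–0.029 |
| 0.0005 | 12.5% | 0.0001–0.0038 | 0.0003–0.0005 |

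In the first dataset 48.5% of the m = 5 seeds gave p<0.05; in the last, all did. Even 100 imputations leave a small spread when p sits on the boundary, so the seed should be written down as well.

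**SF-36 PCS.** In simulations of 1,500 trials per cell at 79–91% power (imputation pooled over arms, 10–15% dropout), MMRM and MI with m = 5 disagreed on p<0.05 in 2.7–4.1% of trials, but MMRM and MI with m = 50 in only 0.6–1.4%. Most of the apparent difference between the two methods is the noise of 5 imputations.

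**The case against.** The strongest reply is that 5 imputations give valid inference. Rubin's method allows for a finite number, and the efficiency loss is only 2–3%. This stands: a reader might infer bias or an inflated type I error, and nothing in the SAP supports that.

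It can also be said that borderline results are unlikely. Protocol 8.2 names DAS28(CRP) and SF-36 PCS among the endpoints with at least 90% power. The note to Table 1 in Protocol 3.0 reports P<0.001 for all key secondary endpoints in the earlier csDMARD study, though it does not name HAQ-DI or SF-36 PCS. This stands too and limits the size. HAQ-DI is absent from the 90% list, but that list is illustrative, so its absence is weak evidence of low power.

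Two stronger readings are tempting. The first is that the SF-36 PCS p-value is undefined because the documents conflict. They do conflict, but the SAP gives one method in 9.2.3 and Table 7, with code in Appendix C. Protocol 8.1 defers the full detail to a SAP finalised before the Period 1 lock. It is an undeclared departure. Nor does the conflict require a move to MI: that would replace a valid, seed-free analysis with a seed-dependent one.

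The second is that the SAP has dropped observed-data checks for the ranked continuous endpoints. A separate observed-case analysis is indeed not listed for them. However, SAP 9.2.4 and Table 7 run MMRM on DAS28(CRP) and on the ACR components, of which HAQ-DI is one, at every visit to Week 12. Appendix C excludes data after study drug discontinuation, as the observed-case definition in 9.1.2 does. For SF-36 PCS, that MMRM is the main analysis.

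**Conclusion.** The point holds for ranks 1 and 2: the SAP leaves avoidable, unrecorded seed noise in two gating p-values. Its reach is narrow. Two seeds would disagree at 0.05 in about 6–7% of trials at effects of 0.22–0.30 SD, 3–4% at about 91% power, and under 0.5% at 0.50 SD. These rates rest on assumed effects, visit correlations and a missing-at-random dropout model with 10–15% missing. Results far from 0.05 are unaffected.

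The SF-36 PCS mismatch is a secondary documentation matter, as is the unlisted observed-case analysis.

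**What to change.** 1. In SAP 9.1.2, raise the number of imputations from 5 to at least 50, preferably 100, and write the seed there. Seed noise in Z falls to about a third (0.049/0.147) or a quarter (0.034/0.147). List the imputation variables at the same time, because a seed reproduces the result only if the model is fixed. Cost: a sentence or two and seconds of computing.
2. For SF-36 PCS, either declare MMRM in the SAP as a change from Protocol 8.1.4.1.2 and 8.1.4.1.5, with a reason, or align the two documents. Either choice is acceptable. Cost: one sentence.
3. Either add the observed-case analysis for the three continuous ranked endpoints, or state that the MMRM on observed on-treatment data serves that purpose. Cost: at most one table.
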